### 2.1.3 Pharmacokinetic variables

The primary endpoint is sarilumab PK exposure ( $C_{\max}$  and  $AUC_{0-\tau}$ ), following first dose, and  $C_{\text{trough}}$  from baseline to week 12.

The PK blood samples will be collected before IMP injection at a given visit according to the schedules of sample collection and at or near the onset and completion of the occurrence of a serious adverse event (SAE). Details can be found in Section 1.2 Study Flow Charts of the protocols [REDACTED]

In the extension part, the main PK parameter will be serum sarilumab  $C_{\text{trough}}$ .

### 2.1.4 Safety endpoints

The safety analysis will be based on the reported adverse events (AEs) and other safety information, such as clinical laboratory data, vital signs, etc. Safety and acceptability assessments (local tolerability) are the primary objectives of the extension part of the studies.

#### *Observation period*

The observation period will be divided into 5 epochs: SCREENING, TREATMENT in core period, TREATMENT in extension period, FOLLOW-UP, and POST-STUDY (defined as below):

- The SCREENING epoch is defined as the time from the signed informed consent date up to the time prior to first dose of IMP.
- The CORE TREATMENT epoch is defined as the time from first dose of IMP to last dose in core phase +13 days for patients on bi-weekly dosing or +6 days for patients on weekly dosing, or first dose of IMP in the extension period for patients who enter the extension.
- The EXTENSION TREATMENT epoch is defined as the time from first dose of IMP in extension period to last dose of IMP in extension period + 13 days for patients on bi-weekly dosing or +6 days for patients on weekly dosing. Only patients who enter the extension have the EXTENSION TREATMENT epoch.
- The FOLLOW-UP epoch is defined as the time from the end of TREATMENT epoch (ie, the end of CORE TREATMENT epoch for patients not entering in the extension period; or the end of EXTENSION TREATMENT epoch for patients who enter the extension period) to “last dose of IMP+60 days”.
- The POST-STUDY epoch is defined as the time after the “last dose of IMP+60 days”.

The entire treatment-emergent adverse event (TEAE) period includes the CORE TREATMENT, EXTENSION TREATMENT (only applicable for patients who enter the extension), and FOLLOW-UP epochs. The TEAE period for the core part includes CORE TREATMENT epoch for patients who enter the extension, and includes CORE TREATMENT and FOLLOW-UP epochs for patients not entering the extension.

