The 12-week core treatment phase is from Visit 2 (Baseline-Week 0) to the time that Visit 12 investigational medicinal product (IMP) is administered. During the 12-week core treatment phase, for the dose-finding and second portions, patients in the lower weight group (Group B: < 30 kg and ≥ 10 kg) will be randomly assigned to the following sarilumab PK sampling Schedule 1 or 2 ([Section 9.1.1](#)) in order to minimize the amount of blood withdrawn and the number of visits while maintaining the evaluation of the primary endpoint:

- Schedule 1: Baseline, Day 3, Day 8, Week 2, Week 4, Week 8, and Week 12
- Schedule 2: Baseline, Day 5, Day 12, Week 2, Week 4, Week 8, and Week 12.

2. An extension phase:

- A 144-week extension for patients enrolled in the dose-finding and second portions: The IMP at Visit 12 is considered as the first IMP for the extension phase. Only patients who have reached a JIA ACR30 response at Visit 12 (Week 12) will be permitted to continue in the extension phase. Patients will continue on the same dose regimen of sarilumab they were assigned to receive in the 12-week core treatment phase of the study until the selected dose regimen is determined. Once the dose regimen is selected, patients who were not already on this dose regimen will have their dose regimen adjusted to the selected dose regimen and will follow a new visit schedule with more frequent monitoring (for PK, safety, and efficacy) for the first 12 weeks compared to those patients who do not have dose regimen adjusted ([Section 1.2.2.2](#)).
- An 84-week extension for patients enrolled in the third portion. The IMP at Visit 12 is considered as the first IMP for the extension phase.

3. End-of-Treatment (EOT) and End-of-Study (EOS):

- For patients enrolled in the dose-finding and second portions: Patients who discontinue the study treatment prematurely will be assessed using the procedure for the EOT at Visit 27. These patients will be asked to return for the end-of-study (EOS) assessment 6 weeks after the EOT visit (EOT + 6 weeks). For patients who discontinue the study treatment during the 12-week core treatment phase, there will be an additional sarilumab PK assessment 2 weeks after the EOT visit (EOT + 2 weeks) and IL-6 and soluble interleukin-6 receptor (sIL-6R) will be measured at EOT visit. These patients will be asked to perform all the protocol scheduled visits and assessments except sarilumab administration until Visit 12.

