11.4.3 Analyses of safety data

Safety data will be summarized descriptively. The summary of safety results will be presented by dose regimen. Further subdivision by weight group will be performed only for selected parameters given the small sample size. Additional methods including the approach to handle the dose-adjustment in safety analyses, safety analyses by time periods, and the exposure-adjusted analyses on safety events will be detailed in the statistical analysis plan.

The safety analysis will be based on the reported AEs and other safety information, such as clinical laboratory data, vital signs, etc. Safety and acceptability assessments (local tolerability) are the primary objectives of the extension parts of the studies (see [Section 9.3](#)).

All safety analyses will adhere to Sanofi “Guideline for the Analysis and Reporting of Safety Data from Clinical Trials.”

Observation period

The observation period will be divided into 5 epochs: Screening, Treatment in core period, Treatment in extension period, Follow-up, and Post-study (defined below):

- The **Screening** epoch is defined as the time from the signed informed consent date up to the time prior to the first dose of IMP.
- The **Core-treatment** epoch is defined as the time from the first dose of IMP to last dose in the core treatment phase + 13 days (or + 6 days for patients on weekly dosing), or first dose of IMP in the extension period for patients who enter the extension phase.
- The **Extension treatment** epoch is defined as the time from first dose of IMP in extension period to last dose of IMP in extension period + 13 days (or + 6 days for patients on weekly dosing). Only patients who enter the extension period have the **Extension treatment** epoch.
- The **Follow-up treatment** epoch is defined as the time from the EOT epoch (ie, the end of **core-treatment** epoch for patients not entering in the extension period; or the end of the **extension treatment** epoch for patients who enter the extension period) to last dose of IMP + 60 days.
- The **Post-study epoch** is defined as the time after the last dose of IMP + 60 days. The rationale of having “last dose of IMP + 60 days” as the end of **follow-up** epoch is to capture the events observed within approximately 5 half-lives of the last IMP.

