The entire TEAE period includes the **core treatment**, **extension treatment** (only applicable for patients who enter the extension), and **follow-up** epochs. The TEAE period in the core treatment phase includes **core-treatment** epoch for patients who enter the extension, and includes **core-treatment** and **follow-up** epochs for patients not entering the extension.

All safety analyses will be performed on the safety population, unless otherwise specified, using the following common rules:

- The baseline value is defined as the last available value prior to the first dose of the study medication.
- The potentially clinically significant abnormality (PCSA) values are defined as abnormal values considered medically important by the Sponsor according to predefined criteria/thresholds based on literature review and defined by the Sponsor for clinical laboratory tests and vital signs.
- The PCSA criteria will determine which patients had at least 1 PCSA during the TEAE period, taking into account all evaluations performed during the TEAE period, including nonscheduled or repeated evaluations. The number of all such patients will be the numerator for the on-treatment PCSA percentage.
- The treatment-emergent PCSA denominator by group for a given parameter will be based on the number of patients assessed for that given parameter in the TEAE period by dose regimen on the safety population.
- For quantitative safety parameters based on laboratory measurements, descriptive statistics will be used to summarize results and change from baseline values by visit and dose regimen. Summaries will include the endpoint value. The endpoint value is commonly defined as the value collected at the same day/time of the last dose of investigational product. If this value is missing, this endpoint value will be the closest one prior to the last dose intake.
- Analyses of the safety variables will be essentially descriptive and no systematic between-group testing is planned.

Adverse events

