Adverse event incidence tables will present the number (n) and percentage (%) of patients in each dose regimen cohort experiencing an AE by primary system organ class (SOC; sorted by internationally agreed SOC order), high-level group term (HLGT), high-level term (HLT) and preferred term (PT) sorted in alphabetical order. Multiple occurrences of the same event in the same patient will be counted only once in the tables within a treatment phase. The denominator for computation of percentages is the safety population within each dose regimen.

All treatment-emergent AESIs will be summarized by AESI category and PT, showing number (%) of patients, sorted by decreasing incidence of PT within each AESI category (see [Section 10.4.4.1](#)).

Death

The incidence of death, if applicable, will be generated on the safety population

Number (%) of patients who died by study period (on-treatment, during follow-up or post-study):

- Death in included but not treated patients
- TEAE leading to death (death as an outcome on the AE CRF page as reported by the Investigator) by primary SOC, HLT, HLT and PT, and by primary SOC and PT, showing number (%) of patients sorted by internationally agreed order of SOC and alphabetic order of HLT, HLT, and PT for the 4-level summary.

Clinical laboratory evaluations

The summary statistics (including number, mean, median, standard deviation, minimum, and maximum) of all laboratory variables (laboratory values and changes from baseline) will be calculated for each visit or study assessment (baseline, each post baseline time point, endpoint) by dose regimen. This section will be organized by biological function.

The incidence of PCSAs and abnormal laboratory values at any time during the TEAE period will be summarized by biological function and dose regimen.

For lipids, the NCEP APTIII classification will be used for the baseline.

The incidence of neutropenia, thrombocytopenia, and lymphopenia by maximal grade will be summarized.

Hepatic disorders

The liver function tests (LFTs), namely AST, ALT, ALP, and total bilirubin are used to assess possible drug-induced liver toxicity. The proportion of patients with PCSA values at any post-baseline visit by baseline status will be displayed by dose regimen for each parameter. The proportion of patients with PCSA values at any post baseline visit may be displayed by duration of exposure for each dose regimen cohort.

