#### 2.4.5 Analyses of safety data

Safety data will be summarized descriptively for each study [REDACTED] separately. The summary of safety results will be presented by dose regimen cohort. Further subdivision by weight group will be performed only for selected parameters given the small sample size.

Safety summaries during the entire TEAE period will be provided. In addition, summaries on the important safety events will also be provided by time periods including 0-12 weeks, 0-24 weeks, and 0-52 weeks; details are provided in [Section 2.4.5.6](#). For the analyses on 0-52 weeks and entire TEAE period, summaries on the non-selected doses will only include the data collected prior to the first dose adjustment to the selected dose; a combined 'any dose' group will be added to summarize all the safety data for all treated patients. In addition, data after the dose adjustment will be summarized separately ([Section 2.4.11](#)).

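### Core-part TEAE percentages are counted over about 84 days for patients who enter the extension but over 60 to 144 days for those who do not, so they are not comparable between regimens with different entry rates

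*SAP*

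**What the plan says.** SAP 2.1.4 (Observation period) ends the core treatment epoch 13 days (q2w) or 6 days (qw) after the last core dose, "or first dose of IMP in the extension period for patients who enter the extension". It then defines a TEAE period for the core part. For entrants this is the core epoch alone. The SAP continues: "and includes CORE TREATMENT and FOLLOW-UP epochs for patients not entering the extension". The follow-up epoch ends 60 days after the last dose. Protocol 11.4.3 repeats the rule, adding the follow-up to the core "epochs for patients not entering the extension", and explains that the 60-day limit "is to capture the events observed within approximately 5 half-lives of the last IMP".

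Entry depends on outcome for part of the trial. Of the dose-finding and second portions, Protocol 6.1 says: "Only patients who have reached a JIA ACR30 response at Visit 12 (Week 12) will be permitted to continue in the extension phase". No such condition is stated for the third portion. The same section fixes the boundary: "The IMP at Visit 12 is considered as the first IMP for the extension phase".

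Adverse event percentages are crude: "The denominator for computation of percentages is the safety population within each dose regimen" (Protocol 11.4.3; SAP 2.4.5.1 agrees). SAP 2.4.5.1 promises events per 100 patient-years only for the entire TEAE period. SAP 2.4.5 adds that "summaries on the important safety events will also be provided by time periods including 0-12 weeks", with 24 and 52 weeks as further cut-offs.

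**The concern.** A crude percentage of patients with at least one event rises with the time over which events are counted. Here that time depends on whether the patient enters the extension, and in the first two portions entry depends on ACR30 response at Week 12. Two regimens with the same event risk but different entry rates would therefore give different core-part percentages. For non-entrants who complete 12 weeks, the additional time also falls after treatment has ended, so the percentage mixes on-treatment and off-treatment experience in proportions that vary by regimen.

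The planned exposure adjustment does not cover this, because it applies to the entire TEAE period. The fixed 0-12-week summaries are announced only for the important safety events, so full tables by system organ class and preferred term are not promised on a common window.

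**Working it through.** **Anchor.** Study day = 7 × week + 1, so Week 12 is 7 × 12 + 1 = Day 85. This matches Visit 12 in the flow chart of Protocol 1.2.1. The documents give no length in days for the core-part TEAE period, so it has to be derived.

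**Windows.** For non-entrants the end is the last dose day + 60. Days elapsed = end day − 1.

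| Patient | Last dose counted | Window ends | Days elapsed |
|---|---|---|---|
| Enters the extension | n/a | first extension dose, Day 85 | 84 (81 to 87 with the widest visit window, ±3 days) |
| q2w completer, not entering, no Visit 12 dose | Week 10, Day 71 | 71 + 60 = Day 131 | 130 |
| qw completer, not entering, no Visit 12 dose | Week 11, Day 78 | 78 + 60 = Day 138 | 137 |
| Dosed at Visit 12, classed as not entering | Day 85 | 85 + 60 = Day 145 | 144 |
| Stops after first dose | Day 1 | Day 61 | 60 |
| q2w, stops after second dose | Day 15 | Day 75 | 74 |

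**Time actually observed.** Adverse events are collected to the end-of-study visit, 6 weeks after end of treatment, which itself falls 2 weeks (q2w) or 1 week (qw) after the last dose. For completers without a Visit 12 dose this is 71 + 14 + 42 = Day 127 (q2w) and 78 + 7 + 42 = Day 127 (qw), or 126 days in both cases.

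**Open classification.** Protocol 1.2.1, footnote j, says ACR30 status reaches the investigator only after Visit 12, and it withholds the Visit 12 injection only from completers who stop for other reasons. Protocol 10.1.7 gives that injection only to patients going on to the extension. Protocol 6.1 counts it as the first extension dose. Depending on the reading, a Week-12 non-responder has 84 days (the dose counts as entry), 130 or 137 days (no dose), or 144 days (dosed but not entering).

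**Effect on incidence (illustration).** Assume a constant hazard through follow-up. If p is the 84-day incidence, incidence at t days is 1 − (1 − p)^(t/84).

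| p at 84 days | at 126 days | at 130 days |
|---|---|---|
| 30% | 41.4% | 42.4% |
| 60% | 74.7% | 75.8% |
| 80% | 91.1% | 91.7% |

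For two regimens with the same hazard and non-entry of 10% versus 40% (assumed shares), the difference is (0.40 − 0.10) × (incidence at t − p):

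- p = 30%: 0.3 × 11.4 to 12.4 points = 3.4 to 3.7 points
- p = 60%: 0.3 × 14.7 to 15.8 points = 4.4 to 4.7 points
- p = 80%: 0.3 × 11.1 to 11.7 points = 3.3 to 3.5 points

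**In patients.** The design has 6 evaluable patients per regimen and weight group, about 12 per dose-finding regimen. The artefact is 12 × 0.033 = 0.4 to 12 × 0.047 = 0.6 of a patient.

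**Exposure adjustment.** Rates divided by duration of exposure would not remove the effect. For a q2w non-entrant, exposure is 71 − 1 + 14 = 84 days and window/exposure is 130/84 = 1.55. For a q2w patient completing 156 weeks (last dose Week 154, Day 1079), it is 1138/1092 = 1.04.

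**The case against.** The strongest reply has five parts.

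- **The follow-up is deliberate.** The 60 days serve a stated purpose, about five half-lives of observation. This stands as a reason to keep the epochs and the overall TEAE summaries. It does not justify mixing window lengths in a 12-week comparison by regimen.
- **The direction is not fixed.** A reader might infer that a less effective regimen will always look less safe. The documents do not support that. Patients who stop in the first weeks have windows of 60 to 74 days, shorter than entrants, and on one reading of the Visit 12 rules non-responders have the same 84 days as responders. Non-comparability stands; a general direction does not.
- **The consequence is small and its use is unproven.** A reader might also infer that these percentages steer dose selection. Protocol 6.1.2 and 6.2.2 describe a committee reviewing PK, PD, efficacy and safety data, and no passage says that a crude core-part percentage decides. Safety analysis is descriptive, and the illustrated shift is under one patient per dose-finding regimen.
- **The remedy may already exist.** SAP 2.4.5.6 is listed in the contents and cited in 2.4.5 for the time-period summaries, but its text is not in the version reviewed. It may apply a Week 12 cut. That full adverse event tables will be run over the core-part TEAE period is also an inference from its definition in 2.1.4. The absence of a correction therefore cannot be asserted.
- **A fixed window is also a convention.** For a patient dosed only on Day 1 it would count to Day 85, 24 days beyond the Day 61 limit. This stands as a trade-off. Protocol 10.3.4 keeps early discontinuers in scheduled follow-up to Week 12, so the data should be there.

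**Conclusion.** The concern holds in limited form. By the stated rule, core-part TEAE percentages are counted over about 84 days for entrants; about 130 days (q2w) or 137 days (qw) for completers who do not enter and have no Visit 12 dose, with about 126 days observed; 144 days if dosed at Visit 12 and classed as not entering; and as little as 60 to 74 days for very early discontinuers. Because entry is tied to ACR30 in the dose-finding and second portions, crude core-part percentages should not be compared between regimens whose entry rates differ.

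The size, about 3 to 5 percentage points, rests on a constant hazard through off-treatment follow-up and on assumed non-entry shares of 10% and 40%. It applies only to tables that use the core-part TEAE period; a summary cut at Week 12 for everyone would not carry it. This is a definition worth tightening, not evidence that the safety comparison or the choice of regimen is wrong.

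**What to change.** Keep the epochs and the overall TEAE period as they are. In SAP 2.1.4, with a matching line in Protocol 11.4.3:

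- For every core-part TEAE table by regimen, not only the important safety events of SAP 2.4.5, count events in one fixed 0-12-week window from first dose (Day 1 to Day 85) for all patients.
- Show non-entrants' later follow-up-epoch events in a separate column.
- If SAP 2.4.5.6 already applies such a cut to all core-part tables, say so in 2.1.4.
- Reconcile Protocol 1.2.1 footnote j, 6.1 and 10.1.7 with SAP 2.1.4 on whether a Week-12 non-responder receives a Visit 12 dose and whether that dose counts as entering the extension. The review takes no position on the dosing rule itself.

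The cost is one more date rule and one extra column. No events are lost, but core-part incidences will no longer include off-treatment follow-up events after Day 85. Where Visit 12 falls up to 3 days early, a few days after the first extension dose will fall inside the window.

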#### **2.1.4.1 Adverse events variables**

##### ***Adverse event observation period***

- Pretreatment AEs are AEs that developed or worsened or became serious during the screening epoch.
- Treatment-emergent AEs (TEAEs) are AEs that developed or worsened or became serious during the treatment and/or follow-up treatment epochs, as applicable.
- Post-study AEs are AEs that developed or worsened or became serious during the post-study epoch.

All AEs (including SAEs and AESIs) will be coded to a lower-level term (LLT), PT, high-level term (HLT), high-level group term (HLGT), and associated primary SOC using the version of MedDRA in effect at Sanofi at the time of DBL.

The occurrence of all AEs (including SAEs and AESIs) will be recorded from the time of signed informed consent until the end of the study.

Any SAE brought to the attention of the Investigator at any time after the end of the study for the patient and considered by him/her to be caused by the IMP with a reasonable possibility, should be reported to the monitoring team.

**Adverse events of special interest:**

Two sets of summaries on adverse events of special interest (AESIs) will be generated:

1. One refers to AESIs for the pediatric program, as defined in the protocols. The AESIs and its search criteria are listed in [Table 4](#).
2. To further ensure that all potential risks are fully evaluated, the AESIs defined in sarilumab adult RA program with search criteria broader than the AESI specified in the protocols will also be summarized. The AESIs and its search criteria are listed in [Table 5](#).

Adverse events of special interest will be flagged in the database using search criteria. All AEs captured on the general AE form and any specific AE forms will be searched.

**Table 4 – Protocol defined AESIs and search criteria**

AESI flag	Search criteria
Clinically significant infections including: 
 
• Opportunistic infections
 
• Tuberculosis
 
	Reported by the investigators on the AE CRF page with AESI box ticked.
Anaphylaxis	
GI diverticulitis and perforation	
Lab abnormalities including: 
 
• ALT increase leading to permanent discontinuation
 
• Grade 4 neutropenia (>10 days after the initial IMP administration) or any neutropenia leading to permanent discontinuation
 
• Thrombocytopenia leading to permanent discontinuation
 
	
[REDACTED]	
[REDACTED]	
[REDACTED]	
[REDACTED]	
Pregnancy a	CRF checkbox: Pregnancy
Overdose a	CRF checkbox: Symptomatic overdose

a Standard AESI applies to all Sanofi studies

